Milwaukee Day Cares Indoor Air Quality Assessment and Educational Response Study

Full study protocol and statistical analysis plan

August 11, 2018

Funded by the Clinical and Translational Science Institute of Southeastern Wisconsin
Award Numbers UL1TR001436, TL1TR001437, and KL2TR001438

Protocol Summary

Purpose

A research and community service partnership, comprising the Medical College of Wisconsin (MCW), UWM College of Nursing, and the non-profit asthma coalition Fight Asthma Milwaukee (FAM) Allies, proposes to describe and improve health-relevant indoor air quality (IAQ) conditions within diverse urban Milwaukee child day care environments. Inferior IAQ could contribute significantly to the development and exacerbation of asthma^{6,7,8} which affects 1 in 10 children in the State⁹. Day care IAQ has been assessed in few studies ^{1,10,11,12,13,14,15,16,17,18,19} and is largely unregulated by Wisconsin state law²⁰.

This project aims to understand the levels of indoor organic pollution and fine particles in the air, as well as temperature and humidity, using inexpensive, consumer-grade, Internet cloud- enabled continuous indoor air quality monitors. These air quality variables are established risk factors for both the development and exacerbation of asthma

Aims

1) Assess baseline IAQ characteristics in urban Milwaukee daycare settings.

- Objective 1.1: Deploy 36 IAQ monitors in 36 childcare settings by November, 2018.
- Objective 1.2: Collect 36 IAQ monitors from 36 daycare settings by February, 2019.
- Objective 1.3: Identify trends based on subtype analysis of IAQ baseline findings between large facility based, small home based and unlicensed daycare settings through data analysis by March 2019.

2) Determine the efficacy of the Green Cleaning for Asthma educational curriculum to alter IAQ and daycare staff cleaning/pest control behaviors objectively.

- Objective 2.1: Deliver Green Cleaning for Asthma classes for staff in 36 daycare organizations by January, 2019.
- Objective 2.2: Implement and collect IAQ pre and post surveys from 1 designated staff member in each of 36 daycare organizations by February, 2019.
- Objective 2.3: Identify trends in relationship to the educational intervention with regards to monitoring device variables including tVOC, PM2.5 and relative humidity variables and composites through data analysis by March 2019.

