- Objective 2.4: Identify behavior changes of daycare staff with regards to cleaning practices, VOC generation as a result of the educational intervention through data analysis by March 2019.

3) Determine the feasibility of a future daycare oriented educational and research program to alter development of asthma and/or asthma exacerbations by improving IAQ.

- **Objective 3.1:** Assess the feasibility of educational training and community deployment of the educational curriculum.
- **Objective 3.2:** Develop proposals to investigate child health within daycare environments to determine future efficacy of IAQ interventions upon health outcomes such as asthma incidence, severity and exacerbations and daycare staff knowledge about asthma and recognition of symptoms of concern.

Research Design

A prospective randomized stepped-wedge trial is proposed. The partnership will engage day care facilities in a 4-month intervention. Half of the facilities will receive education at the second month, allowing the team to assess pre- and post-education air quality readings. The rest of the facilities will receive education at the third month. Devices will be removed from the day cares after the 4th month.

Enrolled day cares will be provided with IAQ monitoring and continuing education-eligible educational programs for day care staff. Nursing students from UWM, an Americorp worker, and MCW community health workers will be trained to provide the curriculum. The groups will be block randomized to start the educational program at either 1 month or 2 months after initial baseline IAQ measurements. Summaries of the findings from the assigned devices will be shared with day care staff at the conclusion of the study.

Two intervention schedules will be implemented:

Group A		Group B	
Month	Outreach	Month	Outreach
1	IAQ monitors deployed, pre survey	1	IAQ monitors deployed, pre survey
2	IAQ education delivered	2	
3		3	IAQ education delivered
4	IAQ monitors collected, post survey	4	IAQ monitors collected, post survey

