Within each intervention group, two cohorts will be determined by licensure per the WI Dept of Children and Families' licensing for the program. Specifically, Licensed Family Child Care Centers provide care for up to eight children (to be referenced as home daycare), Licensed Group Child Care Centers provide care for nine or more children. Other data to be obtained from the daycare will include age of facility, type of heating, presence of air conditioning, type of air filtration, presence of gas ranges/stoves, usual cleaning regimen and cleaners, typical pesticide regimen, whether windows are typically opened, the State Youngstar rating (if a participant), # of children under 5, and over 5 years of age.

Procedures

Educational curriculum: A day care-specific modification of the FAM Allies “Green Cleaning for Asthma” curriculum will be provided to each facility by UWM nursing students, an AmeriCorps worker, FAM Allies volunteers, or MCW staff. Surveys of present cleaning/pesticide practices and air quality inventory will be obtained before and after the educational intervention. One person from each daycare will fill out the pre and post surveys and will receive a \$25 gift card upon completion of the post survey. Each daycare organization will receive a \$25 gift card for coordinating the training and housing the indoor air quality device.

IAQ monitoring: Portable IAQ devices will be deployed within the day care facility to measure variables pertinent to asthma such as total volatile organic compounds (tVOC), particulate matter (PM2.5), temperature, and relative humidity. These consumer-grade monitors are inexpensive, silent, unobtrusive, and upload data continuously via a cellular WiFi hotspot device provided by the study. Continuous data will be tagged with date of the educational intervention, and statistical analysis for trends over time as a result of the intervention will be conducted. Secondary analyses will evaluate which variables and practice changes are associated with improved IAQ.

Timeline providing details of each organization’s role:

April – May, 2018

- Public Allies (AmeriCorps) hiring process
- Flier development and marketing to day care organizations
- Recruitment of day care organizations
- Purchase supplies and contracts: IAQ monitors and hotspots

June, 2018

- FAM Allies volunteer training
- MCW staff training
- FAM Allies/MCW: Deploy 14 IAQ/hotspots in 14 day care organizations (Groups A and B)

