- FAM Allies/MCW: Collect IAQ pre surveys from designated staff member in each of 14 day care organizations (Group A and B)

July, 2018

- FAM Allies/MCW: Teach educational intervention in 7 day care organizations (Group A)

August, 2018

- FAM Allies/MCW: Teach educational intervention in 7 day care organizations (Group B)

September, 2018

- FAM Allies/MCW: Collect 14 IAQ/hotspots from day care organizations (Groups A and B)

- FAM Allies/MCW: Collect IAQ post surveys from designated staff member in each of 14 day care organizations (Group A and B)
- FAM Allies/MCW: Compile data (Groups A and B)
- Public Allies (AmeriCorps) onboarding and training
- UWM nursing student training
- UWM Nursing: Deploy 6 IAQ/hotspots in 6 day care (Groups A2 and B2)
- UWM Nursing: Collect IAQ pre surveys from designated staff member in each of 6 day care organizations (Group A2 and B2)

October, 2018

- UWM Nursing: Teach educational intervention in 3 day care organizations (Group A2)
- Public Allies (AmeriCorps): Deploy 16 IAQ/hotspots in 16 day care organizations (Groups A3 and B3)
- Public Allies (AmeriCorps): Collect IAQ pre surveys from designated staff member in each of 14 day care organizations (Group A3 and B3)

November, 2018

- UWM Nursing: Teach educational intervention in 3 day care organizations (Group B2)
- Public Allies (AmeriCorps): Teach educational intervention in 8 day care organizations (Group A3)

December, 2018

- UWM Nursing: Collect 6 IAQ/hostpots from 6 day care organizations (Groups A2 and B2)
- UWM Nursing: Collect IAQ post surveys from designated staff member in each of 6 day care organizations (Group A2 and B2)
- UWM Nursing: Compile Data (Groups A2 and B2)
- Public Allies (AmeriCorps): Teach educational intervention in 8 day care organizations (Group B3)

January, 2019

- Public Allies (AmeriCorps): Collect 16 IAQ/hotspots from 16 day care organizations (Groups A3 & B3)
- Public Allies (AmeriCorps): Collect IAQ post surveys from designated staff member in each of 16 day care organizations (Group A3 and B3)
- Public Allies (AmeriCorps): Compile data (Groups A3 and B3)

February, 2019

Data compilation and submission to biostatisticians

March, 2019

- Final data reports and reporting to Funder
- Share data reports with all participating day care organizations

References

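### Do a pre-survey count of 14 for a 16-daycare wave, and loose wording on when monitors come out, call for a change to the plan?

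*Combined protocol and SAP*

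**What the plan says.** **Survey count.** The October 2018 timeline entries for Groups A3 and B3 include "Deploy 16 IAQ/hotspots in 16 day care organizations (Groups A3 and B3" and, on the next line, "Collect IAQ pre surveys from designated staff member in each of 14 day care organizations (Group A3 and B3". In January 2019 the same wave has "Collect IAQ post surveys from designated staff member in each of 16 day care organizations (Group A3 and B3". Its classes are listed as 8 daycares in November and 8 in December.

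The overall requirement appears in three other places:

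- Objective 2.2: "Implement and collect IAQ pre and post surveys from 1 designated staff member in each of 36 daycare organizations by February, 2019".
- The schedule table under Research Design, which puts the pre survey in month 1 for both groups.
- Procedures, on the educational curriculum: "One person from each daycare will fill out the pre and post surveys". The same paragraph places the surveys before and after the education.

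**Monitor removal.** The Research Design prose describes a four-month intervention and says "Devices will be removed from the day cares after the 4th month". The table just below it has "IAQ monitors collected, post survey" in the month-4 row for both groups. Daycares are to "start the educational program at either 1 month or 2 months after initial baseline IAQ measurements", which the table shows as months 2 and 3. Objective 1.2 wants all 36 monitors collected by February 2019. The timeline gives months throughout and never days.

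**The concern.** A survey count that disagrees with its own wave is a natural thing to flag. Taken literally, two daycares would give a post survey with nothing to compare it with, and a pre survey missed before the class cannot be recovered later. The document is dated August 2018, so the October wave was still to come.

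The monitor wording looks like a second inconsistency in the same schedule. If month 4 means the start of that month, monitoring lasts about three months and Group B, taught in month 3, has about one month of readings after education. If devices stay for four full months, the figures are about four and two. Aim 2 relates the readings to the education, so the planned length of that window seems to matter.

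**Working it through.** **Step 1: counts by wave, from the timeline.**

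| Activity | A/B | A2/B2 | A3/B3 | Total |
|---|---|---|---|---|
| Monitors deployed | 14 | 6 | 16 | 36 |
| Classes taught | 7 + 7 | 3 + 3 | 8 + 8 | 36 |
| Monitors collected | 14 | 6 | 16 | 36 |
| Post surveys | 14 | 6 | 16 | 36 |
| Pre surveys | 14 | 6 | **14** | **34** |

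Four of the five rows reproduce the plan's figure of 36. The fifth falls short by 36 − 34 = 2, all in one cell. With 16 in that cell the row becomes 14 + 6 + 16 = 36. The stray value equals the first wave's count, which suggests a carried-over line. Read literally, the shortfall is 2/36 = 5.6% of daycares. Three other places rule out that reading.

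**Step 2: month of collection.** Study month = collection month − deployment month + 1.

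- A/B, June to September: 9 − 6 + 1 = 4.
- A2/B2, September to December: 12 − 9 + 1 = 4.
- A3/B3, October to January (counted as month 13): 13 − 10 + 1 = 4.

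All three waves follow the table. Collection at the close of month 4 also fits the prose and the four-month description. The last collection, in January 2019, meets the February date in Objective 1.2.

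**Step 3: how much the unstated day matters.** Taking the first and last days of the scheduled months, across waves:

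| | Any day in month 4 | Last day of month 4 |
|---|---|---|
| Total monitoring | 62–122 days | 92–122 days |
| Group B after education | 1–61 days | 30–61 days |

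The low end of 1 day needs a class on the last day of month 3 and collection the next morning; nothing in the document plans that. Fixing collection to the last day still leaves a spread of about a month, because deployment and class dates are also given only by month. Much of the spread therefore comes from month-level scheduling and not from the two wordings.

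**Step 4: does a fourth month change precision?** The document gives no model or variance components, so this is an assumed bound only. Take monthly periods, wave-by-period effects and a random daycare intercept, and let *r* be the between-to-within-daycare variance ratio. The randomised contrast then comes from month 2, when Group A has been taught and Group B has not. The variance with 3 periods relative to 4 is (1 + 3r)² / [(1 + 4r)(1 + 2r)]:

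- r = 0.1: 1.69/(1.4 × 1.2) = 1.006
- r = 0.5: 6.25/(3 × 2) = 1.042
- r = 1: 16/(5 × 3) = 1.067
- limit for large r: 9/8 = 1.125, so the standard error rises by at most √1.125 − 1 = 6%.

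**The case for a change.** The case for acting is that the wrong digit is certain, sits in a schedule that sets out each organization's tasks, and costs nothing to correct. That is true, and it is a good reason to correct it at the next reissue. It does not make it a fault in the design or analysis. No reader of Objective 2.2, the month-1 row and Procedures would conclude that two daycares are exempt, and wave-3 classes come only in November and December, after the October pre surveys.

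On the monitors, the stronger argument is that the timeline also lists compiling each wave's data in its collection month, which fits awkwardly with last-day collection. This stands as a small untidiness. It does not establish a second removal time: the final compilation and submission to the biostatisticians is set for February 2019, after every wave has closed. A full four months from each deployment would, for October deployments, run to 1–28 February 2019 and so collide with that step. This too favours closing month 4 as the intended reading.

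It is also fair to say that the bound in Step 4 assumes an immediate, constant effect. If the effect built up slowly, Group B's later readings would matter more. The document does not posit this, and each site's actual window can be worked out from its tagged education date and its readings.

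**Conclusion.** The concern does not call for a change to the plan. The count is a clerical slip of 2 (34 listed, 36 required), and the rest of the document settles what is meant. The removal wording is loose but compatible on one natural reading, collection at the close of month 4, which agrees with the table, all three waves and Objective 1.2. What remains is an unstated day within a month, a detail the field team and analysts can handle from actual dates.

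No loss of survey pairs and no bias is shown. Any effect on precision is small: under the assumed model, 0% to 12.5% in variance even if a whole month were lost. This rests on two assumptions: that field staff collect a pre survey from every enrolled daycare, as three other places require, and that collection does not systematically fall in the first days of month 4.

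### In every wave the team that teaches the class also collects the post surveys, which feed a pre/post change with no untaught comparison

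*Combined protocol and SAP*

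**What the plan says.** The Timeline divides the 36 day cares into three waves, each run by one team: Groups A and B (FAM Allies/MCW), A2 and B2 (UWM Nursing), and A3 and B3 (Public Allies, AmeriCorps).

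- **Wave 1.** The July 2018 entry reads "FAM Allies/MCW: Teach educational intervention in 7 day care organizations (Group A"). One month later the same team teaches the seven Group B sites. Its survey task comes in September 2018: "FAM Allies/MCW: Collect IAQ post surveys from designated staff member in each of 14 day care organizations (Group A and B"). The same team compiles the data that month.
- **Wave 2.** The October 2018 entry reads "UWM Nursing: Teach educational intervention in 3 day care organizations (Group A2"), with the three B2 sites taught in November. The survey task comes in December 2018: "UWM Nursing: Collect IAQ post surveys from designated staff member in each of 6 day care organizations (Group A2 and B2"). The compilation task for that month is given as "UWM Nursing: Compile Data (Groups A2 and B2").
- **Wave 3.** Public Allies teaches eight A3 sites in November and eight B3 sites in December. In January 2019 it collects 16 post surveys, followed by "Public Allies (AmeriCorps): Compile data (Groups A3 and B3").

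The biostatisticians first appear in February 2019, when the compiled data are submitted to them.

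Under Procedures, one person per day care completes both surveys, which cover cleaning and pesticide practices. The monitors "upload data continuously via a cellular WiFi hotspot device provided by the study". The schedule table under Research Design puts the pre survey in month 1 and the post survey in month 4 for both groups, with education in month 2 (Group A) or month 3 (Group B). The plan mentions no blinding, no independent collector and no separation of teaching from data handling.

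**The concern.** Aim 2 sets out to judge the curriculum's effect on air quality and on staff behaviour objectively. Behaviour is measured by self-report, and the completed form goes back to the team that taught which practices are preferred. Before the class there is no taught answer to give; afterwards there is. Any wish to please the team would therefore act mainly at the post survey and would look like adoption of the taught practices.

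This bears directly on Objective 2.4, which looks for behaviour change attributable to the class. It also reaches the secondary analyses under Procedures that relate practice changes to improved air quality, since those use the same answers. A lesser concern is that the people compiling the monitor data know when each site was taught.

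**Working it through.** No power or sample size figure is involved. The check is whether the pattern holds in every wave, and which comparison it affects.

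**1. Who does what (Timeline, June 2018 to January 2019)**

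| Wave | Team | Sites taught | Post surveys collected | Compiles |
|---|---|---|---|---|
| 1 (A, B) | FAM Allies/MCW | 7 + 7 = 14 | 14 | same team |
| 2 (A2, B2) | UWM Nursing | 3 + 3 = 6 | 6 | same team |
| 3 (A3, B3) | Public Allies | 8 + 8 = 16 | 16 | same team |
| Total | | 36 | 36 | 3 of 3 waves |

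14 + 6 + 16 = 36, which matches the 36 settings in Objective 1.1. No wave or site is an exception.

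**2. Which comparison is exposed**

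- At the month 4 post survey Group A was taught in month 2 and Group B in month 3. No site is still untaught.
- No survey falls between the two teaching dates, so the staggered start gives the survey no taught-versus-untaught contrast.
- The survey result is therefore post minus pre within sites. A pressure that arises after teaching goes straight into that difference.
- Within each wave the same team serves both groups, so the A-versus-B comparison is less affected.

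**3. What can still be changed**

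The plan is dated August 11, 2018.

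- Wave 1 pre surveys were scheduled for June 2018, before that date; wave 1 post surveys fall in September, after it.
- Wave 2 pre surveys are due in September 2018 and wave 3 pre surveys in October 2018.
- Both surveys can use a new route at 6 + 16 = 22 sites (22/36 = 61%). At 14 sites (14/36 = 39%) only the post survey can.

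The October 2018 line for A3 and B3 lists pre surveys from 14 organizations, against 16 monitors deployed that month and 16 post surveys in January. The 22 assumes that all 16 wave 3 sites give a pre survey; those lines need reconciling.

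**4. Size**

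The documents give no figure from which the bias could be estimated. An assumed percentage of respondents shading their answers would only return the same percentage as its result, so none is offered.

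**The case against.** The strongest reply has five parts.

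- **Tasks go to organisations, not people.** Wave 1 is run by two organisations with volunteers and staff, and wave 2 by nursing students in the plural. A different team member could collect at these 20 sites (14 + 6). Only wave 3 points to one person, since Research Design and Procedures each name a single AmeriCorps worker. A reader might infer that respondents hand the form to their own instructor. The plan does not say so, nor that the respondent attended the class. What stands is that nothing prevents it.
- **Collecting is not rating.** The staff member fills in the form and the team retrieves it. A reader might infer that unblinded educators assess the outcome; the documents do not support that.
- **The monitor data are automatic.** Compiling is not defined, and no text gives field teams authority over gaps, outliers or exclusions. A reader might infer that educators can shape the readings, but this is not shown. The remaining point is that their handling is unnecessary.
- **The survey is uncontrolled and self-reported whoever collects it.** This is correct. Only the increment due to the collecting team is at issue here, and a sealed envelope removes no more than that.
- **Changing route midway has a cost.** This is also correct: wave 1 would have different routes before and after. It calls for disclosure and separate reporting.

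Having one team per wave also suits a small community partnership that is assessing feasibility (Objective 3.1). That explains the arrangement, but does not require forms to return through the teaching team.

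**Conclusion.** The concern holds in limited form. In 3 of 3 waves and at 36 of 36 sites, the team that teaches also collects the post surveys and compiles the data. Because every site has been taught by month 4, pressure to please that team would inflate the pre/post change behind Objectives 2.2 and 2.4. The direction is predictable and the size is unknown.

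Two assumptions underlie this: that the respondent was reached by the teaching, and that the respondent expects the team to see the answers. Both are reasonable for a class given to that site's staff, but neither is stated. The exposure of the monitor data (Objective 2.3) is secondary. The documents do not support a claim that the randomised comparison of air quality is biased by this arrangement. The change is worth making because it is cheap, not because the results would otherwise be invalid.

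**What to change.** 1. **Survey lines in the Timeline.** The respondent returns the form online or in a sealed envelope, marked with a site code only, directly to the biostatisticians, and is told that the teaching team will not see the answers.
2. **Waves 2 and 3 (22 sites).** Use this route for both the pre and the post survey.
3. **Wave 1 (14 sites).** Use it for the September 2018 post survey and record that the pre survey was scheduled for collection by the team. Report the pre/post change separately for wave 1 and for waves 2 and 3. Do not read a difference between them as the effect of the route, since the waves also differ in team and season.
4. **Monitor data (secondary).** Replace the compilation lines with a direct export of the raw cloud data to the biostatisticians, who decide on gaps and outliers before group and class date are merged in. The plan has no written rules for these decisions, so they should be set down first.

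**Cost.** An online form or envelopes, and cloud access for the biostatisticians, with no extra staff expected; the plan does not say whether they already have that access. Some late surveys will need chasing, which the existing $25 gift card on completion helps. Someone must confirm completion for the card without seeing the answers. Pre and post routes will differ at the 14 wave 1 sites.
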